APPENDIX G. PREGNANCY PREVENTION AND REPORTING

AG-CLI-0209 is a study in with older population, however due to not having sufficient reproductive toxicity data for the study product, per (Guideline on Risk Assessment of Medicinal Products on Human Reproduction and Lactation: from Data to Labelling, EMEA/CHMP/203927/2005), proper pregnancy prevention and planning needs to be in place. Women who have recently been assessed as post-menopausal (<18 months) should have Follicle-stimulating hormone (FSH) and estradiol levels measured to confirm the post-menopausal state.

Pregnancy prevention

In accordance with good clinical practice, to avoid embryo-fetal exposure, AG-CLI-0209 has a risk evaluation and mitigation strategy to prevent pregnancy in subjects on study product. These measures help to minimize the possibility of fetal exposure to the investigational product due to the unknown risk to the health of the fetus and/or the pregnant woman.

Precautions include:

- Exclusion of women with child bearing potential on the AG-CLI-0209 study.
 - Women who are surgically sterile. For the purposes of this study, only women with hysterectomy or bilateral oophorectomy will be considered surgically sterile. Tubal ligation alone is not sufficient to be considered sterile.
 - Women who have documented primary ovarian insufficiency (premature ovarian failure) who are 55 years of age or younger will be given a urine pregnancy test within 7 days of Day 0, Month 3, Month 9 and Month 12 to ensure that they are not pregnant.
 - Confirmation of menopause by history of amenorrhea for 18 months or greater in the absence of other causes of amenorrhea, serum FSH (30 mIU/mL or higher) and serum estradiol (30 pg/mL or less) both consistent with menopause.
 - A pregnancy test should be conducted at screening. If pregnancy is confirmed prior to the start of the trial in general, the subject should not be enrolled in the trial.
- Male subject commitment to using a reliable method(s) of contraception, and/or abstinence, for the duration of therapeutic product exposure (up to 12 weeks post last study product dose). Please note that any pregnancy confirmed post that period will need to be documented up to the completion of the follow up period. (Reference Pregnancy Reporting below). As required, contraception should be extended beyond the last dose of the investigational product.

Contraception Methods

Male subjects must commit to use a highly effective method of contraception throughout treatment cycles through 12 weeks post last study dose. Effective methods include:

- Vasectomy
- Sexual Abstinence
- Barrier Methods (male or female condom with spermicide)

Pregnancy reporting

Subjects (female and male) should be advised to report, immediately, to the Investigator a suspected or confirmed pregnancy that occurs in the course of this clinical trial (including during any period of exposure that may exceed the length of the trial).

Pregnancy of a female subject or female partner of a subject must be reported within 24 hours of clinical research site awareness.

A female subject must discontinue study drug immediately and the investigator should report all pregnancies to the Sponsor, using the paper Pregnancy Report Form and SAE form. Please note that any pregnancy confirmed during investigational product exposure will need to be documented up to the completion of the follow up period.

Pregnancy of the female partner of a male subject that is within 12 weeks of last dose of study product should be reported to the investigator. The investigator should report the pregnancy to the Sponsor, using the paper Pregnancy Report Form and SAE form. Please note that any pregnancy confirmed during investigational product exposure will need to be documented up to the completion of the follow up period.

Pregnancy exposure to a female partner of a male subject after 12 weeks of last dose of study product should be reported to the investigator. The investigator should report the pregnancy to the Sponsor, using the paper Pregnancy Report Form only. This pregnancy should not be reported as an SAE.

Follow-up

Follow-up procedures regarding the course of the pregnancy should be discussed with the subject, as appropriate. Follow-up should be done by the investigator throughout the pregnancy and for an appropriate period thereafter. If the pregnancy is experienced by the female partner of a male subject, informed consent will be requested for follow up information.

The outcome of each pregnancy should be recorded and followed-up. For live births, longer term follow-up of a child is recommended, when possible and appropriate.

Miscarriages, Congenital anomalies, and birth defects should be reported as an SAE. Any complication occurring during pregnancy that meets the criteria for SAE should be reported in the SAE form.

This statistical analysis plan (SAP) provides a comprehensive and detailed description of strategy, rationale, and statistical methods to be used to assess clinical efficacy and safety. The purpose of the SAP is to ensure the credibility of the study findings in the pre-specified statistical approaches to the analysis of study data prior to the database lock. This SAP provides additional details concerning the statistical analysis outlined in the protocol.

2 Investigational Plan

A phase 3 study AG-CLI-0206 was planned as a registration study and received Special Protocol Assessment (SPA) approval by the U.S. Food and Drug Administration (FDA). Prior to undertaking the phase 3 study, a pilot study will confirm the feasibility of the study-related activities in study AG-CLI-0206 and the tolerability of the dosage regimen of AMG0001.

2.1 Study Objectives

The primary objectives of the clinical trial are:

1. To confirm the feasibility of study-related activities and the tolerability of a modified dosage regimen of AMG0001 in CLI
2. To evaluate the safety of AMG0001

Additional visits for HGF protein and HGF plasmid DNA sample collection will be conducted on Day 4 and Month 12+4 days for all subjects, and additionally HGF plasmid DNA assay sample collection on Month 9+4 days for the first 5 enrolled subjects (i.e. subjects who receive any study treatment). Long-term safety follow-up data using a questionnaire will be obtained every 6 months following the Month 18 visit at the Month 24, Month 30 and Month 36 time points. Subject data collection during the Long Term Follow-up (LTFU) period (post-Month 18 visit) will be limited to Serious Adverse Events (SAEs) and the visit questionnaire data intended to assess the occurrence of any potential gene-therapy related delayed AEs. The total duration of the study will be up to 37 months.

Subjects will not be eligible to receive the subsequent doses of the study product if major amputation of the index leg has occurred, where the index leg is defined at the leg with the greater severity of CLI disease (also referred to as the treated leg or affected leg).

All eligible subjects will receive AMG0001 intramuscularly in the muscles of the index leg based on the location of disease.

Schedule of Study Procedures

PROCEDURES	Study Day (visit window*) - Visit # (V)	Screening Period	Dosing Visits: First Cycle												Dosing Visits: Second Cycle												Post-Month 18 Long Term Follow-up															
			Days -30 to -1				Day 0 - V1				Day 14 ($\pm 2d$) - V2				Day 28 ($\pm 2d$) - V3				Month 3 ($\pm 7d$) - V5				Month 3+14 Days ($\pm 2d$) - V6				Month 3+28 Days ($\pm 2d$) - V7				Month 3+42 Days ($\pm 2d$) - V8				Follow-Up		Follow-Up		Follow-Up		Follow-Up	
*d=days																																										
Subject Consent & Medical History	X																																									
Vital Signs, Weight & Height ⁽³⁾	X	X	X	X	X	X	X	X	X	X	X	X	X	X	X	X	X	X	X	X	X	X	X	X	X	X	X	X	X	X	X											
12-Lead ECG	X																																									
Physical Examination ⁽⁶⁾	X ⁽¹⁰⁾	X ⁽¹⁰⁾	X ⁽¹¹⁾	X ⁽¹¹⁾	X ⁽¹¹⁾	X ⁽¹⁰⁾	X ⁽¹¹⁾	X ⁽¹¹⁾	X ⁽¹¹⁾	X ⁽¹⁰⁾	X ⁽¹⁰⁾	X ⁽¹⁰⁾	X ⁽¹⁰⁾	X ⁽¹⁰⁾	X ⁽¹⁰⁾	X ⁽¹⁰⁾	X ⁽¹⁰⁾	X ⁽¹⁰⁾	X ⁽¹⁰⁾	X ⁽¹⁰⁾	X ⁽¹⁰⁾	X ⁽¹⁰⁾	X ⁽¹⁰⁾	X ⁽¹⁰⁾	X ⁽¹⁰⁾	X ⁽¹⁰⁾	X ⁽¹⁰⁾	X ⁽¹⁰⁾	X ⁽¹⁰⁾	X ⁽¹⁰⁾	X ⁽¹⁰⁾	X ⁽¹⁰⁾										
Peripheral Vascular Intervention Update ⁽⁶⁾	X ⁽¹⁾	X ⁽¹⁾																																								
CLI Assessment ⁽⁷⁾	X ⁽¹⁾	X ⁽¹⁾																																								
Hemodynamic Measurements ^(6,7)	X ⁽¹⁾	X ⁽¹⁾																																								
Angiogram ⁽⁷⁾	X																																									
QOL (VascuQOL) ^(6,7)		X																																								
VAS (pain scale) ^(6,7)	X ⁽¹⁾	X ⁽¹⁾																																								
Ulcer Tracings	X ^(1,2)	X ⁽¹⁾																																								
Ulcer Photos ^(4,7)	X ^(1,2)	X ⁽¹⁾																																								
Retinopathy Exam ⁽⁶⁾	X																																									
HbA1C and FBG	X																																									
Urine Pregnancy Test ^(6,8)	X	X																																								

PROCEDURES	Study Day (visit window*) – Visit (V) *d=days	Screening Period	Dosing Visits: First Cycle										Dosing Visits: Second Cycle					Follow-Up	Post-Month 18 Long Term Follow-up							
			Days -30 to -1	Day 0 - V1	Day 14 (±2d) - V2	Day 28 (±2d) - V3	Day 42 (±3d) - V4	Month 3 (±7d) - V5	Month 3+14 Days (±2d) - V6	Month 3+28 Days (±2d) - V7	Month 3+42 Days (±2d) - V8	Month 6 (±7d) - V9	Month 7.5 (±5d)	Month 9 (±7d) - V10	Month 9+14 Days (±2d) - V11	Month 9+28 Days (±2d) - V12	Month 9+42 Days (±2d) - V13	Month 12 (±7d) - V14	Month 12+14 Days (±2d) - V15	Month 12+28 Days (±2d) - V16	Month 12+42 Days (±2d) - V17	Month 15 (±7d) - V18	Month 16.5 (±5d)	Month 18 (±7d) - V19	Month 24	Month 30
FSH and Estradiol testing ⁽⁹⁾	X																									
Hematology, Chemistry, Urinalysis ⁽⁶⁾	X	X				X						X	X													
Anti-HGF Antibodies Assay ⁽⁶⁾		X				X						X	X													
Study product administration		X	X	X	X	X	X	X	X	X	X		X	X	X	X	X	X	X	X	X	X				
Injection site photos		X	X	X	X	X	X	X	X	X	X	X	X	X	X	X	X	X	X	X	X					
Adverse Events ⁽⁷⁾		X	X	X	X	X	X	X	X	X	X	X	X	X	X	X	X	X	X	X	X	X				
Concomitant Medication ⁽⁷⁾	X	X	X	X	X	X	X	X	X	X	X	X	X	X	X	X	X	X	X	X	X	X				
Telephone Contact												X										X				
LTFU Questionnaire																								X	X	X

- (1) Procedures required for assessment of CLI status and ulcers must be conducted during screening ≥ 14 days prior to Day 0 and Pre-dose at Day 0. Stability of CLI must be confirmed by the investigator prior to dosing on Day 0.
- (2) Photos of largest ulcer on the index leg as well as a photo or photos (if necessary) of the entire index leg to show all ulcer/gangrene locations. Debridement should be performed prior to these evaluations;
- (3) Height obtained at Screening only
- (4) Ulcer healing of the largest ulcer on the index limb (determined at Screening) will be assessed clinically by the Investigator by direct visual inspection at each study visit. If the largest ulcer on the index leg heals during the study period the subject should be brought and re-evaluated 2 weeks after healing to confirm it has remained healed and ulcer photography must be completed at that time.
- (5) Photos of largest ulcer on the index leg as well as a photo or photos (if necessary) of the entire index leg to show all ulcer/gangrene locations. Debridement should be performed prior to these evaluations, if necessary.
- (6) Conduct pre-dose when obtained during a dosing visit.
- (7) Procedure must be performed prior to a planned interventional treatment (revascularization or amputation) while on study.
- (8) Urine pregnancy tests will be performed prior to dosing on all women aged 55 years or less. For women who have been determined as premenopausal and are not surgically sterile, per the study requirements will continue with the scheduled urine pregnancy tests throughout the course of the study.
- (9) Performed on all women under the age of 55
- (10) Complete physical exam should be performed. If a dosing visit, perform prior to dosing.
- (11) Abbreviated physical exam should be performed. If a dosing visit, perform prior to dosing.

Schedule of Sample Collection for the Serum HGF Protein & PCR for HGF Plasmid Assays

Study Day	Day 0	Day 4	Day 14	Day 28	Day 42	Month 3	Month 3 + 14 Days	Month 3 + 28 Days	Month 3 + 42 Days	Month 6	Month 9	Month 9 + 4 Days	Month 9 + 42 Days	Month 12	Month 12 + 4 Days	Month 12 + 42 Days	Month 15
Serum HGF protein Assay	X*	X	X*	X*	X*	X*			X*		X*			X*	X		X
PCR for HGF plasmid DNA Assay	X*	X	X*	X*	X*	X*	X*	X*	X*	X	X*	X**	X*	X*	X	X*	X

*At Dosing Visits (indicated by the shaded column), two (2) samples should be drawn one pre-dose and a second drawn four (4) hours post dosing.

**The first 5 subjects who are enrolled will have a blood sample drawn for HGF Plasmid DNA sampling 4 days following their Month 9 Visit.

2.4 Statistical and Analytical Procedures

2.4.1 General Statistical Considerations

This study is not powered for statistical inference, and any testing will be considered descriptive and exploratory. All data summarized in tabular form will have accompanying listings. Figures may also be provided.

Unless otherwise noted, the term “descriptive statistics” will refer to frequency and percent (%) for categorical data and number of observations (n), mean, standard deviation (SD), median, minimum, and maximum for continuous data.

Biodata (serum HGF protein) values reported as below the level of quantitation (10 copies/ uL) will be reported as BLQ and excluded in calculation of the mean and SD.

All analyses will be conducted using SAS 9.4 or later.

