HUV	Human Umbilical Vein

IBC	Institutional Biosafety Committee
IC	Intermittent Claudication
IM	Intramuscular
IRB	Institutional Review Board
ITT	Intention To Treat
IV	Intravenous
K	Potassium
kg	Kilogram
KM	Kaplan Meier
LDH	Lactic Acid Dehydrogenase
LDL	Low Density Lipoprotein
LLOQ	Lower limit of quantification
LOCF	Last observation carried forward
MedDRA	Medical Dictionary for Regulatory Activities
MI	Myocardial Infarction
mm	Millimeter
mg	Milligram
mmHg	Millimeters of Mercury
MRA	Magnetic resonance angiogram
Na	Sodium
NIH	National Institutes of Health
OBA	Office of Biotechnology Activities (Division of the National Institutes of Health)
PAD	Peripheral Arterial Disease
PAP	Papanicolaou
PCR	Polymerase Chain Reaction
PI	Principal Investigator
PSA	Prostate-specific antigen
PTA	Percutaneous Transluminal Angioplasty
PTFE	Polytetrafluoroethylene
QA	Quality Assurance
QC	Quality Control
QOL	Quality of Life
SAE	Serious Adverse Event
SD	Standard Deviation
SFA	Superficial Femoral Artery
TAO	Thrombo-angiitis Obliterans
TBI	Toe Brachial Index
TcPO2	Transcutaneous Oxygen Tension
VAS	Visual Analogue Scale
VEGF	Vascular Endothelial Growth Factor
VSMC	Vascular Smooth Muscle Cells
WBC	White Blood Cell

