2.5.6 PK Analyses

A listing with summary statistics (n, mean, SD, min, and max) will be provided for Serum HGF protein, and a listing of PCR for HGF plasmid DNA Assays will be provided.

For Anti-HGF antibody and confirmation from fusion test, the antibody indication (Yes/No) and fusion test result (Yes/No, if available) will be presented on one listing.

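### SAP 2.4.1 gives serum HGF protein a quantitation limit in copies per microlitre, so the protein limit is undefined, and drops BLQ values, which raises the mean if any occur

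*SAP*

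**What the plan says.** SAP 2.4.1 (General Statistical Considerations) covers "Biodata (serum HGF protein) values reported as below the level of quantitation (10 copies/ uL") and says that such values "will be reported as BLQ and excluded in calculation of the mean and SD". The same section makes the default statistics "number of observations (n), mean, standard deviation (SD), median, minimum, and maximum for continuous data".

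SAP 2.5.6 (PK Analyses) sets its own, shorter list for the protein: "A listing with summary statistics (n, mean, SD, min, and max) will be provided for Serum HGF protein". For the plasmid it plans only "a listing of PCR for HGF plasmid DNA Assays will be provided".

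The sample-collection schedule in SAP 2.2 keeps the protein assay and the plasmid PCR on separate rows. At dosing visits "two (2) samples should be drawn one pre-dose and a second drawn four (4) hours post dosing". The Protocol's list of abbreviations expands LLOQ as "Lower limit of quantification", but neither document gives a value for it.

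**The concern.** There are two separate defects.

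- **The limit is not a protein limit.** A protein assay reports a concentration. A count of copies per microlitre belongs to a nucleic-acid assay, and the plasmid PCR is the only assay in the plan that it fits. The SAP therefore states no usable limit for the one analyte it summarises.
- **The handling rule biases the mean.** BLQ values are the low end of the distribution. If they are removed, the mean describes only the quantifiable subjects, and different time points can rest on different subjects. Section 2.5.6 has no median and no BLQ count that would show this in the table.

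The samples are paired around dosing, so a reader will naturally compare pre-dose with post-dose means. If pre-dose values are more often BLQ, exclusion raises the pre-dose mean more than the post-dose mean, and a real rise will usually look smaller than it is.

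**Working it through.** **1. Which assay can the rule act on?** Both readings fail.

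| Reading | Consequence |
|---|---|
| The analyte is right, the unit is wrong | Protein has an exclusion rule but no stated limit |
| The unit is right, the analyte is wrong (PCR meant) | The rule changes no mean or SD, because PCR is only listed, and protein has no BLQ rule |

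**2. How many summaries are exposed?** In the SAP schedule, protein is drawn before and after dosing at eight visits (Days 0, 14, 28 and 42; Month 3; Month 3+42 days; Month 9; Month 12) and once each on Day 4, at Month 12+4 days and at Month 15. That is 8 × 2 + 3 = 19 time points.

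**3. Direction.** Every dropped value is below the limit and every kept value is at or above it. The kept mean therefore exceeds the full mean whenever a time point has at least one of each. No distribution is needed for this. Example, assuming 3 BLQ values and a kept mean of 2 × LLOQ:

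- n = 10: the full mean lies between (7×2 + 3×0)/10 = 1.4 and (7×2 + 3×1)/10 = 1.7 LLOQ, an overstatement of 18% to 43%.
- n = 8: the full mean lies between 1.25 and 1.625 LLOQ, an overstatement of 23% to 60%.

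**4. Size under a distribution.** The documents give no BLQ fraction, HGF level or spread, so these are assumptions: log-normal values, s = ln(GSD), and LLOQ at quantile p with normal deviate z_p. Then

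reported mean / true mean = Φ(s − z_p) / (1 − p).

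For GSD 2, s = 0.6931:

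- p = 20%: Φ(0.6931 + 0.8416)/0.8 = 0.9376/0.8 = 1.17
- p = 50%: Φ(0.6931)/0.5 = 0.7559/0.5 = 1.51
- p = 80%: Φ(0.6931 − 0.8416)/0.2 = 0.44098/0.2 = 2.20

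Ratios to the true value at 20 / 50 / 80% BLQ:

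| GSD | Mean, BLQ dropped | SD, BLQ dropped | Mean, LLOQ/2 |
|---|---|---|---|
| 1.5 | 1.12 / 1.31 / 1.66 | 0.92 / 0.87 / 0.85 | 0.96 / 0.89 / 0.85 |
| 2 | 1.17 / 1.51 / 2.20 | 1.00 / 1.05 / 1.18 | 0.98 / 0.95 / 1.00 |
| 3 | 1.22 / 1.73 / 3.01 | 1.07 / 1.24 / 1.63 | 1.00 / 1.00 / 1.15 |

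The mean error is always upward. The SD error can go either way.

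**5. Effect on a pre/post comparison.** Suppose values truly double after dosing and the GSD stays at 2. The ratio of reported means is 2 × (post-dose inflation)/(pre-dose inflation):

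- pre-dose 20% BLQ: 2 × 1.028/1.172 = 1.75
- pre-dose 50% BLQ: 2 × 1.135/1.512 = 1.50
- pre-dose 80% BLQ: 2 × 1.426/2.205 = 1.29

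Across GSD 1.5 to 3 the ranges are 1.75-1.80, 1.50-1.56 and 1.29-1.34. With LLOQ/2 the same doubling appears as 1.76 to 2.26 over the whole grid.

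**6. Number left.** At 80% BLQ, 0.2 × 8 = 1.6 to 0.2 × 10 = 2.0 subjects are expected to be quantifiable. The chance of at most one quantifiable value, which leaves no SD, is 0.8^8 + 8(0.2)(0.8^7) = 0.50 for n = 8 and 0.8^10 + 10(0.2)(0.8^9) = 0.38 for n = 10.

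**The case against.** The strongest reply is that only the labelling error is certain. If the sentence was meant for the PCR assay, no rule drops protein values and no mean is biased. That is correct, but protein is then left with no BLQ rule, so the text still needs correcting.

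The rule could also be read as following the status that the laboratory reports, with the protein limit held in assay documents. That may make it workable in practice. The SAP neither states nor cites such a limit, though, and the one it does state cannot be applied to protein.

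Several points on impact stand:

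- The size rests wholly on assumptions. The 80% BLQ case has no support in the documents, and the true effect could be zero.
- SAP 2.5.6 plans no pre/post contrast, change from baseline or test for protein, and no objective uses it. The attenuation figures describe how the table would be read, not a planned analysis.
- Listings keep each BLQ record visible, and with 8-10 subjects they can be counted by hand. They do not correct the table, and the SAP does not say whether n, minimum and maximum include BLQ values.
- Leaving out the median is a permitted departure from the default. It matters because a ranked median copes with BLQ values better than a mean does.
- LLOQ/2 is not uniformly better for the SD. Its SD ratio is 0.93 to 1.18 over the grid. At GSD 1.5 it is 1.11 and 1.18 at 20% and 50% BLQ, against 0.92 and 0.87 under exclusion, so it is slightly worse there.

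**Conclusion.** The concern holds. The unit error and the absence of a protein limit are certain from the text. The upward bias is certain in direction if the rule is applied to protein as written and a time point has both BLQ and quantifiable values. Its size is unknown: zero with no BLQ values, and 1.12 to 3.01 times the true mean over the assumed grid (log-normal, GSD 1.5 to 3, 20% to 80% BLQ). The consequence is confined to a descriptive PK table in a pilot study; it touches no test and no study objective. It should be corrected, but it does not threaten the study's conclusions on feasibility, tolerability or safety.

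**What to change.** In SAP 2.4.1, state the protein assay's LLOQ in concentration units, and have the sponsor confirm whether 10 copies/uL belongs to the plasmid PCR assay. In SAP 2.5.6, for HGF protein at each time point:

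- report n and the number and percent BLQ;
- report the median with BLQ values ranked lowest;
- if a mean is shown, keep BLQ values in it by a pre-specified convention such as LLOQ/2, and name that convention in the table.

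The cost is SAP wording and one table-shell change, with no new data. The downside is that substitution is itself approximate: LLOQ/2 gives 0.85 to 1.15 times the true mean over the grid, though it is nearer than exclusion in all nine cases. The BLQ count and the ranked median need no substituted value, so they should carry the interpretation.

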2.4.2 Missing Data

For endpoints involving the VascuQoL assessment, non-missing data after revascularization or major amputation will be included in analysis, and missing values for subjects who are dead at the time point of interest will be scored as 0.

For the Visual Analogue Scale (VAS), each subject’s data after revascularization or major amputation will be imputed using the value of the last available assessment prior to intervention, and the worst score available will be imputed for assessments after death.

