4.11. Ischemic Rest Pain Measurement

The severity of rest pain based on the average over the previous 7 days will be recorded using the 10 cm visual analog scale (VAS) (see Appendix E). The VAS score must be documented at all visits and prior to any planned intervention (revascularization or major amputation). In order to assess rest pain adequately, the use of pain medication/opioids must be specifically documented in the CRF during the VAS evaluation period. The subject should not be allowed to see his previous rest pain measurements nor should the score be revealed to him/her.

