8.1.2. SAEs Associated with Worsening CLI

Serious Adverse Events relating to the worsening of CLI that occur in the index limb such as gangrene, cellulitis or osteomyelitis, are related to the study disease and are symptoms/signs of progression of study disease will not be recorded as serious adverse events (unless the speed or extent of the symptoms/signs are unexpected based on the natural history or bear a strong temporal relationship to the study product as determined by the Investigator). Data on the subject's CLI status of the index limb will be recorded in detail on non-AE CRFs and is not required to be documented as an SAE. Frequently worsening of CLI may lead to hospitalization followed by local or systemic treatment or surgical intervention (minor amputation, surgical revascularization or major amputation). The entries for the above events will be made in the CLI section of the CRF. However, in the case of serious intercurrent illness or systemic complications like septicemia, multi-organ failure, or pneumonia, these events will be captured in the AE or SAE section of the CRF.

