2.5.5 Efficacy Analysis

- Ulcer improvement**

A table showing the number of subjects completely healed in the target ulcer will be provided at up to 6 months, > 6 months to 12 months, from >12 months to 18 months. If available, the number of subjects with at least 20% reduction in bi-dimensional size (by measuring largest diameters) will be provided. The reduction in bi-dimensional size will be calculated by taking the product of the largest diameters for each baseline and postbaseline measurement, then subtracting the baseline result from the postbaseline result.

- Ischemic Rest pain (of the index leg) using a 10 cm VAS scale**

Rest pain severity will be assessed at the specified predetermined time points. Rest pain severity will also be assessed prior to surgical revascularization or major amputation (of the index leg). A table showing the number of subjects reduced by ≥ 20 mm from baseline in VAS score will be provided at up to 6 months, > 6 months to 12 months, from >12 months to 18 months. Summary statistics will be provided for baseline and change from baseline for each visit and LOCF. One sample t-test for change-from-baseline will be performed. If death occurs, the worst score prior to death instead of last observation will be carried forward.

- Hemodynamic Measurements**

Summary statistics will be provided for baseline and change from baseline for hemodynamic parameters (right/left brachial systolic pressure, ankle systolic pressure measured at dorsalis pedis and posterior tibial, toe systolic pressure, calculated ABI, and calculated TBI) by visit. At each visit, only subjects who have a non-missing value at both baseline and the specific visit will be summarized. Two-sided one-sample t-test will be performed for each visit and LOCF.

- Subjects with any worsening CLI event of index leg**

A summary table and listing of worsening CLI-related events of the index leg including any new or worsening events, worsening rest pain, new ulcer or worsening ulcer, new or worsening wound infection, peripheral vascular intervention, complication of a peripheral vascular intervention, cellulitis, and amputation due to worsening CLI will be provided.

- Subjects who either died, had MI, Stroke, revascularization (by surgical bypass, by endovascular intervention, by hybrid procedure), major amputation, or all-cause death**

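### Carrying forward the pre-intervention VAS can keep an amputated or revascularized subject in the rest-pain responder count for later intervals

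*SAP*

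**What the plan says.** **Imputation.** For the VAS, SAP 2.4.2 states that each subject's "data after revascularization or major amputation will be imputed using the value of the last available assessment prior to intervention". The rule covers observed as well as missing values and is not tied to any one table. After death, SAP 2.4.2 says "the worst score available will be imputed for assessments after death", and SAP 2.5.5 says "the worst score prior to death instead of last observation will be carried forward". For VascuQoL, by contrast, SAP 2.4.2 keeps observed scores after an intervention.

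**Responder table.** For rest pain of the index leg, SAP 2.5.5 gives the "number of subjects reduced by ≥ 20 mm from baseline in VAS score" for the periods "up to 6 months, > 6 months to 12 months, from >12 months to 18 months". It has no exclusion or failure rule for subjects with an intervention. SAP 2.5.1 keeps everyone who had at least one injection in the analysis.

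**Protocol.** Section 9.1 item 7 counts subjects with a fall of 20 mm or more, or complete relief, cumulatively at 6, 12 and 18 months. Section 9.2.2 contains a similar pre-intervention carry-forward, attached to the one-sample t-test on change from baseline.

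**Score before an intervention.** Protocol 4.11 says "The VAS score must be documented at all visits and prior to any planned intervention". SAP 2.4.3 bars measurements from unscheduled visits from serving as post-treatment values.

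**The concern.** The endpoint is pain in the index leg. After a major amputation that leg is gone, and after a bypass or endovascular procedure its pain reflects the procedure as well as AMG0001. A carried score that met the 20 mm threshold before the procedure still meets it at every later visit. The Month 12 and Month 18 entries could therefore include subjects whose limb had since been lost or revascularized, and the table would not show it. With 8 to 10 subjects and no control arm, one such subject visibly changes the result.

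**Working it through.** The plan states no figure for this endpoint, so there is none to reproduce. The check applies the written rules to constructed profiles.

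**Inputs from the documents**
- Threshold: a fall of at least 20 mm (SAP 2.5.5).
- Visit days 90, 182, 273, 365, 455 and 548 (SAP Table 2).
- N = 8 to 10 (SAP 2.2).
- Higher VAS means worse pain (Protocol Appendix E).

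**Assumed profile, for illustration only**
- Baseline 70 mm, Month 3 score 45 mm, major amputation of the index leg on day 120.

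**Test at each later visit:** responder if baseline − carried value ≥ 20 mm.

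| Case | Carried value | Fall from baseline | Status at Months 6, 12, 18 |
|---|---|---|---|
| A. Pre-operative VAS 48 | 48 | 70 − 48 = 22 | Responder at all three |
| B. Pre-operative VAS 75, used | 75 | 70 − 75 = −5 | Non-responder at all three |
| C. Pre-operative VAS 75, dropped as unscheduled | 45 (Month 3) | 70 − 45 = 25 | Responder at all three |
| D. As A, death on day 300; worst score includes baseline | 48, then 70 | 22, then 70 − 70 = 0 | Responder at Month 6 only |
| D. As A, death on day 300; worst score post-baseline only | 48 throughout | 22 | Responder at all three |

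A and B show that the direction depends on the last usable score. C shows that SAP 2.4.3, applied literally, could discard the score that records the worsening. D shows that the death rule settles the matter only if the worst score includes baseline, which the SAP does not say.

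**Effect of a non-response rule on case A.** The Month 3 fall of 25 mm was measured before the procedure, so it stands for the interval to Month 6. The two later intervals become non-response. The subject is then a responder in 1 of 3 intervals instead of 3 of 3.

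**Size.** Shift in the responder percentage = k/N for k such subjects, with all treated subjects in the denominator.

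| k | N = 10 | N = 9 | N = 8 |
|---|---|---|---|
| 1 | 10.0 | 11.1 | 12.5 |
| 2 | 20.0 | 22.2 | 25.0 |
| 3 | 30.0 | 33.3 | 37.5 |

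The documents give no intervention rate or response rate, so k is unknown. The range 1 to 3 is an assumption.

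**Dependence on the definition.** Assume N = 10 with four responders by Month 6. Two of them are amputated between Months 6 and 9 with carried values still at least 20 mm below baseline; the other two stay responders, and no new ones appear.
- Status per interval with the carried value: 4/10 in each later interval.
- Status per interval with non-response after the intervention: 2/10 in each.
- Protocol cumulative count: 4/10 at Months 12 and 18, with or without the carry-forward.

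**The case against.** The case for leaving the rule alone has several parts.

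- **Cumulative count.** Under Protocol 9.1 item 7 an early responder stays counted whatever happens later. The SAP intervals could also be read as the time of first response, counting each subject once. This stands: the effect in later intervals requires reading the table as status per interval. The SAP does not say which reading applies.
- **Direction.** A reader might infer that the rule always flatters AMG0001. The documents do not support that. The rule also stops relief from a bypass, or from removal of the painful limb, being credited to the product. It fixes as non-responders those whose last prior score was less than 20 mm below baseline.
- **Pre-intervention VAS.** The required score should often capture worsening. This stands in part, but the requirement covers planned interventions only, and SAP 2.4.3 does not exempt the score. A reader might also take Protocol 8.1.2 ("Frequently worsening of CLI may lead to hospitalization followed by local or systemic treatment or surgical intervention") as evidence that limbs are lost while pain is below baseline. That section concerns safety recording and says nothing about pain levels.
- **Visibility and weight.** SAP 2.5.5 separately tabulates amputation, revascularization, death and worsening CLI, and SAP 2.4.1 provides listings. The objectives are feasibility, tolerability and safety, and all testing is exploratory. This limits the harm, but it does not correct the responder count.
- **Pre-specification.** Protocol 9.2.2 does provide for a carry-forward, but in the sentence on the change-from-baseline t-test. Confining the rule to that summary is consistent with the protocol.

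**Conclusion.** The point holds, with conditions. A subject is counted as an index-leg responder after the leg was amputated or revascularized if four things are true: the responder table uses the imputed values, it reports status per interval, the last usable prior score was at least 20 mm below baseline, and the subject is alive. SAP 2.4.2 is general and SAP 2.5.5 makes no exception, so the first is the natural reading, though it is not stated outright.

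Each such subject shifts the percentage by 10 to 12.5 points. How many there would be cannot be derived from the documents. The count is favourable relative to a treatment-failure rule, not necessarily relative to observed scores.

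In the worked example a reader might infer that 2/10 is the true response and 4/10 an error. It is not: 2/10 is the count under a definition that treats intervention as non-response, which the documents do not adopt. In a descriptive pilot this is a cheap improvement and does not threaten the study's conclusions.

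**What to change.** In SAP 2.5.5:
- Define the responder table as status in each interval. Score assessments after index-leg major amputation, index-leg revascularization or death as non-response, and keep the subject in the denominator. Responses measured before the procedure stand for their own interval.
- Reconcile this with Protocol 9.1 item 7. If the cumulative count is also shown, report beside it how many of its responders later had an intervention.
- Keep the carried pre-intervention value only for the mean-change and LOCF summary, with the number of imputed values beside each mean.

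In SAP 2.4.3, state that the VAS required before an intervention is exempt from the exclusion of unscheduled measurements.

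**Cost.** A few sentences in the SAP and a small programming change. The responder count may be slightly less favourable, and pain relief after a procedure is not counted.
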